3.0 Abbreviation

ALP	Alkaline Phosphatase
ALT	Alanine Aminotransferase
AST	Aspartate Aminotransferase
CTC(AE)	Common Terminology Criteria (for Adverse Events)
Depatux-M	Depatuxizumab mafodotin
EGFR	Epidermal Growth Factor Receptor
GGT	Gamma-glutamyl transferase
Gy	Gray
MedDRA	Medical Dictionary for Regulatory Activities
MGMT	O6-methylguaninemethlytransferese
NCI	National Cancer Institute
OSE	Ocular side effect
PT	Preferred Term
RANO	Response Assessment in Neuro Oncology
RT	Radiation Therapy
SAE	Serious Adverse Event
SAP	Statistical Analysis Plan
SAS	Safety Analysis Set
SGPT	Serum glutamic-pyruvic transaminase
SGOT	Serum glutamic-oxaloacetic transaminase
SOC	Standard of Care
TE(AE)	Treatment Emergent Adverse Event
TMZ	Temozolomide

4.0 Introduction

This abbreviated statistical analysis plan (SAP) will provide detailed statistical methods for the analysis of efficacy and safety data collected in Study M16-534 as outlined in Protocol Amendment 4 (dated 28 May 2019) and will describe analysis conventions to guide the statistical programming work.

The INTELLANCE-1 interim efficacy analysis results (based on data cut of 30 April 2019) overall indicated no survival benefit for adding depatuxizumab mafodotin to standard RT/TMZ therapy in newly diagnosed GBM patients. Based on the results from INTELLANCE-1, it was decided to stop further enrollment into Study M16-534 (UNITE) and collection of efficacy data. At the time of this decision, a total of 40 subjects had been enrolled in Study M16-534 (UNITE). With these changes, no statistical tests are planned to be performed for efficacy endpoints for this study. Given only a small number of patients are enrolled in the study and most of them did not have long-term follow-up, exploratory efficacy endpoints will not be summarized. All summary results will be presented by treatment arm along with the overall results.

All analyses will be performed using SAS Version 9.4 or higher (SAS Institute, Inc., Cary, NC 27513) under the UNIX operating system. The SAP will be signed off before database lock.

5.0 Study Objectives, Design and Procedures

5.1 Objectives

Primary objective

Estimate the percentage of subjects in each prophylactic treatment arm who require a change in ocular side effect (OSE) management due to inadequate control of OSEs.

Secondary objectives

Assess the effects of intervention with bandage contact lenses (BCL) on visual acuity for subjects who require intervention due to inadequate control of OSEs.

5.2 Study Design

5.2.1 Study Design and Design Diagram

[figure not shown]
This is a Phase 3b open-label, randomized, exploratory study to evaluate the effect of 3 ophthalmologic prophylactic treatment strategies for the management of OSEs in subjects with newly diagnosed, EGFR-amplified GBM who are being treated with depatuxizumab mafodotin in addition to standard frontline treatment with chemoradiation (RT/TMZ) followed by adjuvant TMZ. Approximately 90 subjects were planned to be randomized to one of the three following prophylactic eye treatment arms in a 1:1:1 fashion:

- Arm A (SS) – Standard Steroids
- Arm B (SS/VC) – Standard Steroids + Vasoconstrictor + Cold Compress
- Arm C (ES/VC) – Enhanced Steroids + Vasoconstrictor + Cold Compress

During the Chemoradiation Phase, all subjects should undergo focal RT. TMZ should be administered orally from start of RT to the last day of RT for a maximum of 49 days. All subjects should receive depatuxizumab mafodotin once every 2 weeks during this period. The start of the first cycle during the Adjuvant Phase should be scheduled approximately 28 days after the last day of chemoradiation. During the Adjuvant Phase, all subjects should receive oral TMZ for 6 – 12 cycles (depending on local standard of care) and depatuxizumab mafodotin for 12 cycles. Adjuvant treatment should be discontinued upon determination of tumor progression as defined by Response Assessment in Neuro-Oncology (RANO) Working Group criteria, unacceptable toxicity, or refusal to continue study treatment.

Subjects should receive OSE prophylaxis during both the Chemoradiation and Adjuvant Phases as long as depatuxizumab mafodotin treatment is ongoing. For subjects who demonstrate inadequate control of OSEs with the initial prophylactic strategy, intervention with a BCL should first be employed. Subjects who continue to demonstrate inadequate response to BCL intervention should be eligible for unrestricted OSE management according to investigator discretion. Subjects who discontinue depatuxizumab mafodotin for any reason will receive regular follow-up for assessment of AEs at post-treatment 35 and 49 day follow-up visits and, if necessary, assessments of CEAE and ophthalmologic examinations until resolution of OSEs.

Figure 1. Schema of Study Design

5.3 Endpoints

5.3.1 Primary Endpoint

The primary endpoint is defined as the percentage of subjects with either a ≥ 3 -line decline from baseline ($\geq +0.3$ on LogMAR scale) (Bailey IL, Lovie-Kitchin, 2013) in

visual acuity (with baseline correction determined at the screening ophthalmology visit) or \geq Grade 3 OSE severity on the Corneal Epithelial Adverse Event (CEAE) scale, either of which will indicate inadequate control of OSEs requiring a change in OSE management strategy. The primary endpoint is assessed over 8 weeks after initiation of depatuxizumab mafodotin treatment regardless of phases.

5.3.2 Secondary Endpoints

Following secondary endpoints will be assessed:

- Maximum change from baseline on LogMAR scale
- Time to BCL intervention
- Cumulative dose of depatuxizumab mafodotin received (mg/kg) (during chemoradiation and during adjuvant treatment)

5.3.3 Other Safety Endpoints

Non-ocular AEs, laboratory profiles, and vital signs will be assessed throughout the study.

6.0 Analysis Populations

All the analyses will be carried out on the safety population. The **safety population** will comprise all randomized subjects who have received at least 1 dose of Depatux-M. Subjects will be classified according to prophylactic treatment received. The safety population will be the primary analysis population for analysis of all endpoints.

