3 STUDY OBJECTIVES AND ENDPOINTS

3.1 Objectives

Primary Objective

1. Estimate the percentage of subjects in each prophylactic treatment arm who require a change in OSE management due to inadequate control of OSEs.

Secondary Objective

2. Assess the effects of intervention with bandage contact lenses (BCL) on visual acuity and OSE symptom severity for those subjects who require intervention due to inadequate control of OSEs.

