3.3 Secondary Endpoints

Secondary endpoints will be assessed as below over 8 weeks after initiation of depatuxizumab mafodotin treatment, assessed separately for the chemoradiation phase and adjuvant phase, as appropriate, as different doses of depatuxizumab mafodotin are used in each phase. The effectiveness of the initial prophylactic strategy and of the BCL-intervention will be assessed separately, as will be resolution of OSEs after interruption/discontinuation of depatuxizumab mafodotin.

Effectiveness of Prophylactic Regimen	Effectiveness of BCL Intervention

 • Maximum change from baseline on LogMAR scale • Time to BCL intervention • Dose interruptions due to OSEs (% subjects) • Dose reductions due to OSEs (% subjects) • Cumulative dose of depatuxizumab mafodotin received (mg/kg) (during chemoradiation and during adjuvant treatment) • CEAE grade, at each visit 	
 • Change in LogMAR (pre- to post-intervention, then followed longitudinally) • Recovery to < 3-line decline from baseline (< +0.3 LogMAR) in visual acuity (% subjects) • Dose interruptions due to OSEs (% subjects) • Dose reductions due to OSEs (% subjects) • Time to restart depatuxizumab mafodotin (if interrupted) • CEAE grade, at each visit, post BCL intervention
Resolution of OSEs	

 • Time to OSE symptom resolution after drug discontinuation (reversibility) • Time to re-initiation of depatuxizumab mafodotin after dose interruption 	

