The start of the first cycle during the Adjuvant Phase will be scheduled approximately 28 days after the last day of chemoradiation; the AbbVie TA MD should be notified if Adjuvant Phase treatment is to be started more than 42 days after the last day of chemoradiation. All subjects will receive oral TMZ 150 – 200 mg/m² once daily on Days 1 – 5 of each 28-day cycle for 6 – 12 cycles (6 – 12 months) as per local standard prescribing practice. Subjects receive depatuxizumab mafodotin as a 30- to 40-minute infusion at 1.25 mg/kg on Day 1 and Day 15 of each 28-day cycle for a total of 12 cycles (12 months).

OSE Prophylaxis

Subjects will receive OSE prophylaxis during both the Chemoradiation and Adjuvant Phases as long as depatuxizumab mafodotin treatment is ongoing.

Subjects will be randomized to one of the following prophylactic eye treatment arms. Equivalent steroid or vasoconstrictor medications may only be used with pre-approval by the AbbVie Therapeutic Area Medical Director.

Arm A (Standard Steroid)

- Steroid Eye Drops (for example, Prednisolone acetate 1% suspension), 1 drop in each eye 3 times per day starting 2 days prior to depatuxizumab mafodotin infusion and continuing until 4 days after infusion, for a total of 7 days.
- Use of Prednisolone acetate is strongly recommended as the initial steroid eye drop due to the greater potency. Alternative steroids eye drops (for example, 0.1% dexamethasone phosphate solution, or equivalent) may be used if prednisolone acetate is not tolerated.

Arm B (Standard Steroid/Vasoconstrictor and Cold Compress)

- Steroid Eye Drop (for example, Prednisolone acetate 1% suspension), 1 drop in each eye 3 times per day starting 2 days prior to depatuxizumab mafodotin infusion and continuing until 4 days after infusion, for a total of 7 days.
- Use of Prednisolone acetate is strongly recommended as the initial steroid eye drop due to the greater potency. Alternative steroids eye drops (for example, 0.1% dexamethasone phosphate solution, or equivalent) may be used if prednisolone acetate is not tolerated.

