- Cold compress: Starting 5 minutes prior to start of infusion and continuing for 30 minutes past end of infusion; then at least 2 hours total/day during remainder of infusion day and for 2 days after infusion. The cold compress should be applied in increments no longer than 30 min (could be shorter if the patient is uncomfortable).

With the exception of care measures described below as allowed at any time, other prophylactic or supportive measures are not allowed during the initial prophylaxis phase, unless prior approval is obtained from the AbbVie Medical Monitor.

Bandage Contact Lens (BCL) Intervention

If any subject in Arm A, Arm B, or Arm C has a ≥ 3 -line loss in visual acuity ($\geq +0.3$ change from baseline by LogMAR) OR a CEAE \geq Grade 3 ocular side effect, the subject will then receive BCL intervention in addition to the assigned initial prophylactic regimen.

With the exception of care measures described below as allowed at any time, additional measures besides BCL and the original prophylactic regimen are prohibited during the BCL intervention phase, unless prior approval is obtained from the AbbVie Medical Monitor.

Investigator Discretion

Subjects who have a \geq Grade 3 CEAE event despite/after addition of BCL intervention to the initial prophylactic regimen will enter the Investigator Discretion phase, at which point there will be no restrictions on prophylactic or supportive measures used for OSE management.

Subjects who complete 8 weeks of adjuvant therapy (8 weeks after the first adjuvant dose of depatuxizumab mafodotin) will be allowed to enter in the Investigator Discretion phase regardless of CEAE Grade, visual acuity or BCL intervention.

Supportive Care Measures Allowed at Any Time

The following supportive care measures are allowed at any time, regardless of the current phase of OSE management:

- Lubricant Eye Drops
- Artificial Tears
- Antibiotics
- Sunglasses

Information on other allowable medications (prior to eligibility for the Investigator Discretion phase) may be described in the Operations Manual.

Please reference Section 5 "Study Drug" of the Operations Manual for more information on treatments administered in this study.

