5.8 Randomization/Drug Assignment

All subjects will be assigned a unique identification number by the Interactive Response Technology (IRT) at the screening visit. For subjects who rescreen, the screening number assigned by the IRT at the initial screening visit should be used. The IRT will assign a randomization number that will encode the subject's treatment group assignment according to the randomization schedule generated by the statistics department at AbbVie.

Subjects will be randomized in a 1:1:1 ratio to 1 of 3 prophylactic eye treatment regimens (Arm A, Arm B, or Arm C), as described in Section 4.1.

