7.2 Definition for Analysis Populations

The intent-to-treat (ITT) population will comprise all randomized subjects regardless of whether they receive study treatment (depatuxizumab mafodotin) or steroid-related OSE treatment. Since the

primary endpoint is a safety endpoint, the ITT will be used only for summary of enrollment and randomization.

The safety population will comprise all randomized subjects who have received at least 1 dose of depatuxizumab mafodotin. Subjects will be classified according to steroid-related treatment received. The safety population will be the primary analysis population for analysis of all endpoints including efficacy and safety endpoints.

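### SAP 6.0 groups every endpoint by the eye prophylaxis received, so no outcome is clearly planned by randomised arm, although the eye regimen is the only randomised factor

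*SAP*

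**What the plan says.** **What is randomised.** Protocol 5.8 states: "Subjects will be randomized in a 1:1:1 ratio to 1 of 3 prophylactic eye treatment regimens". Operations Manual 5.3 gives every subject the same planned dose of depatuxizumab mafodotin, so nothing else differs by allocation.

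**What the endpoints measure.** The primary objective in Protocol 3.1 reads: "Estimate the percentage of subjects in each prophylactic treatment arm who require a change in OSE management". In Protocol 3.3 one column of secondary endpoints is headed "Effectiveness of Prophylactic Regimen". It includes maximum LogMAR change, time to bandage contact lens (BCL) intervention and cumulative dose, the three that SAP 5.3.2 keeps.

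**How subjects are grouped.** SAP 6.0 carries out all analyses on randomised subjects with at least one dose of Depatux-M, and says: "Subjects will be classified according to prophylactic treatment received". It makes this population primary for all endpoints. The SAP defines no as-randomised set. Protocol 7.2 takes a similar line and gives as its reason that the "primary endpoint is a safety endpoint, the ITT will be used only for summary of enrollment and randomization".

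**What the outcome sections say.** SAP 4.0 promises summaries by treatment arm and overall. SAP 11.2 and 11.3 also report by treatment arm. None of them says whether this is the assigned or the received arm.

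**Where deviations appear.** SAP 9.1 counts, as disposition, subjects whose prophylaxis differed from the randomised one and subjects who had none. SAP 8.4 lists eye-drop use with investigator-assessed compliance.

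**The concern.** Grouping by treatment received is customary for adverse event tables. Here, though, the ocular outcome is also the effectiveness outcome of the randomised intervention, so calling it a safety endpoint does not remove the reason to compare subjects as allocated.

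The trial is open-label and the regimens are largely self-administered. A subject who does not follow the assigned regimen may differ in tolerance or prognosis from one who does. Moving that subject to another column changes the numerator or the denominator, or both, in two arms, possibly for a reason related to the outcome. The disposition table would show how many subjects deviated. It would not let a reader recover the ocular results by assigned arm.

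At stake is bias in the per-arm estimates and in the informal comparison that readers will make between them.

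**Working it through.** **Step 1. Which grouping rule governs.**
- SAP 6.0 is explicit: regimen received, for all endpoints.
- SAP 4.0, 11.2 and 11.3 use treatment arm without defining it.
- SAP 5.2.1 introduces Arms A, B and C as the arms to which subjects were to be randomised, but it describes the design and sets no analysis rule.
- SAP 9.1 separates randomised from received regimen, but only for disposition counts.

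The one stated analysis rule is therefore 6.0, and nothing overrides it.

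**Step 2. The plan's own precision figure.** Protocol Table 6 gives 95% intervals for n = 30 per arm. The Wald formula p ± 1.96 × √(p(1 − p)/n) reproduces all four rows:
- 8/30: 26.7% (10.8, 42.5)
- 10/30: 33.3% (16.5, 50.2)
- 12/30: 40.0% (22.5, 57.5)
- 14/30: 46.7% (28.8, 64.5)

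These depend only on n and the event count, so the choice of grouping does not alter the table. Enrolment stopped at 40 (SAP 4.0), and 40/3 is about 13 per arm if allocation was even. With 5 of 13 failing, the same formula gives 38.5% (12.0, 64.9).

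**Step 3. Effect of one reclassified subject.** The documents give neither a deviation count nor event counts, so the following are assumptions: 13 dosed subjects per arm, e failing in each of Arms A and C, no true difference, and one subject randomised to C but classified to A.
- Failing subject: (e + 1)/14 − (e − 1)/12. At e = 5 this is 6/14 − 4/12 = 42.9% − 33.3%, which is 9.5 points before rounding.
- Non-failing subject: e/14 − e/12. At e = 5 this is 5/14 − 5/12 = 35.7% − 41.7% = −6.0 points.
- 95% half-width of the difference as randomised: 1.96 × √(2p(1 − p)/13). At p = 5/13 this is 37.4 points.

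| Failing per arm (e of 13) | Failing subject moved | Non-failing subject moved | Half-width |
|---|---|---|---|
| 4 | +10.7 | −4.8 | 35.5 |
| 5 | +9.5 | −6.0 | 37.4 |
| 6 | +8.3 | −7.1 | 38.3 |

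At e = 5 one subject is worth 6.0/37.4 = 16% to 9.5/37.4 = 25% of the half-width, in either direction.

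**Step 4. At the planned size.** With 30 per arm and 12 failing in each, one failing subject moved gives 13/31 − 11/29 = 4.0 points. One non-failing subject moved gives 12/31 − 12/29 = −2.7 points. Early closure has made each such subject weigh more.

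**Step 5. The null case.** If every dosed subject received the assigned regimen, both groupings give the same tables.

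**The case against.** The strongest reply is that this is a declared convention. Protocol 7.2 gives its reason openly and the SAP follows it. The aim is estimation within each arm, and SAP 11.2 plans no between-arm test. That stands in part: this is neither a departure from the protocol nor a type I error problem. It does not answer the point that these endpoints judge the randomised regimens.

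A second reply is that treatment arm in SAP 11.2 and 11.3 may well mean the randomised arm, given SAP 5.2.1. That is possible. It is why the claim is that such summaries are not clearly planned, rather than that they are excluded.

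Three stronger readings are tempting, and the documents do not support them.

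- *Subjects can move to another arm's regimen within the primary window.* Protocol 5.7 does say that "other prophylactic or supportive measures are not allowed during the initial prophylaxis phase, unless prior approval is obtained from the AbbVie Medical Monitor". An approved extra measure is not a switch between Arms A, B and C, and nothing says that it would change a subject's group. Unrestricted addition of enhanced steroids or vasoconstrictors belongs to the Investigator Discretion phase, which follows failure despite BCL or 8 weeks of adjuvant therapy (Protocol 5.7, 6.3). The main primary summary is limited to 8 weeks from first dose and to the time before BCL. What remains there is unplanned deviation.
- *The protocol's rule cannot tell Arm A from Arm B.* Protocol 7.2 says "Subjects will be classified according to steroid-related treatment received", and both arms use the same drops: "1 drop in each eye 3 times per day starting 2 days prior to depatuxizumab mafodotin infusion and continuing until 4 days after infusion". But Protocol 2.2 keeps the statistical section only as a record of the original plan and refers the analysis to an abbreviated SAP, whose wording covers the whole prophylactic regimen. This is at most an editorial note.
- *Some dosed subjects will have no group.* The SAP 9.1 row for no prophylaxis sits under all randomised subjects and may hold only undosed ones. The lack of a definition of regimen received is a missing detail and is not itself evidence of bias.

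**Conclusion.** The point holds as a minor one. For the endpoints that evaluate the only randomised factor, the stated grouping rule does not preserve randomisation, and no summary by assigned arm is clearly planned. The textual facts are firm; the effect on results is unknown, because no deviation count is given.

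Under the assumed 13 per arm with 4 to 6 failing in each, one reclassified subject shifts a between-arm difference by 4.8 to 10.7 points, in either direction. Half-widths there are 35.5 to 38.3 points, so the shift is small beside sampling error. With no deviations it is zero. A reader might infer that the trial's comparison is already compromised; the documents do not show that any subject was, or would be, reclassified.

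**What to change.** Before database lock, amend SAP 6.0, 11.2 and 11.3 as follows.

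- Keep the dosed safety population for all analyses.
- Summarise the primary endpoint (SAP 11.2, before BCL), the SAP 11.3 endpoints and cumulative Depatux-M dose by randomised arm, and say so where those sections refer to treatment arms.
- Define regimen received as the initial prophylactic regimen, and state where a dosed subject with no prophylaxis would be shown.
- Use grouping by regimen received only for a sensitivity summary or for adverse event tables labelled as such. Corneal epithelial events feed both the primary endpoint and the adverse event tables, so print the grouping on each table.
- Optionally, as an editorial matter, note that the SAP wording replaces the steroid-related phrase in Protocol 7.2.

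The cost is SAP wording and table labels. The assigned arm comes from the IRT randomisation (Protocol 5.8), and no new data are needed.

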7.0 Analysis Conventions

7.1 Definition of Baseline

Unless otherwise specified, the baseline observation is defined as the last non-missing measurement collected prior to the first dose of any study drug (RT, TMZ and Depatux-M).

7.2 Dealing with Multiple Values on the Same Day

In cases multiple values are collected on the same day at baseline or post-baseline visit the worst value will be used for further analyses.

7.3 Definition of Treatment Emergent Observation

For safety assessments, Treatment Emergent (TE) observations are defined as all newly occurring or worsening safety observation with onset at or following the initiation (date and time) of any study drug and no later than 49 days after the last dose of Depatux-M. If an incomplete onset date is collected for an AE, the AE will be assumed to be treatment-emergent unless there is enough information confirming that is it not (e.g., a month and year is available that precedes the treatment start date).

7.4 Definition of Study Days and Rx Days

Study Day of any observation is defined for post-randomization observations as:

$$\text{Study Day} = \text{Date of observation} - \text{Date of randomization} + 1,$$

and for observations predating randomization as:

$$\text{Study Day} = \text{Date of observation} - \text{Date of randomization}.$$

Thus, the day of randomization is defined as Study Day 1, while the day prior to the randomization is defined as Study Day -1 (there is no Study Day 0).

Study Treatment (Rx) Day of any post-baseline observation is defined as the number of days from the day of the first dose of any study drug (RT, TMZ, and Depatux-M) to the date of observation. It is calculated for each post-treatment observation as follows:

$$\text{Study Rx Day} = \text{Date of observation} - \text{Date of first dose of any study drug} + 1$$

